2.1 Interim Analysis

No interim analysis is planned.

2.2 Final Analyses

The final planned primary analyses will be performed after the completion of the following sequential steps:

1. All participants who have completed the study as defined in the protocol.
2. All required database cleaning activities have been completed and database has been locked.

3. All criteria for un-blinding the randomization codes have been met and the randomization codes have been distributed.

3 Considerations for data analyses and Data Handling Conventions

3.1 Baseline Definition

For parameters height, weight, BMI, height for age Z score (HAZ), individual diversity dietary score (IDDS), carbohydrate, fat and energy from 24 hour dietary recall assessments conducted at screening visit will be considered as baseline and for all other endpoints the baseline value will be the latest pre-dose assessment Visit 2 with a non-missing value.

Unless otherwise stated, if baseline data is missing no derivation will be performed and will be set to missing.

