| 
 • Change from baseline in levels of micronutrients Vitamin A, B12, D (25-hydroxycholecalciferol), E, folate, of the trace elements selenium, zinc, copper, and iron as determined by blood draw and analysis. | 
 • Levels of micronutrients Vitamin A, B12, D (25-hydroxycholecalciferol), E, folate, of the trace elements selenium, zinc, copper, and iron at baseline and end of study. |
| 
 • Change from baseline levels of ferritin, | 
 • Levels of ferritin, sTfR, CRP, |

| | |
|---|--|
| serum transferrin receptor (sTfR), C-reactive protein (CRP), and Alpha 1-acid glycoprotein (AGP) as determined by blood draw and analysis. | and AGP at baseline and end of study. |
| 
 Change from baseline (measured at screening) in dietary diversity score, assessed through 24-hour Individual Dietary Diversity Score (IDDS). | 
 Dietary diversity score assessed through 24-hour IDDS at screening and end of study. |
| 
 Change from baseline (measured at screening) in energy, protein, carbohydrates and fat consumption, assessed through 24-hour dietary recall survey. | 
 Intake of energy, protein, carbohydrate, and fat from 24-hour dietary recall survey at screening and end of study. |

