Change from baseline of each assessment will be analysed using the ANCOVA model with cluster (school) as a random effect; product group and gender as fixed effects; baseline assessments for each responses as a covariate.

Adjusted means, intracluster correlation, 95% confidence intervals, within product group p-values for each product group, product group difference, 95% confidence interval of the difference and the between-product group p-values based on the statistical model will also be presented ([Table 14.2.12.2](#)).

The assumptions of normality and homogeneity of variance will be investigated and violation of these assumptions may be overcome using suitable transformation (eg., log or square root) or by performing appropriate non-parametric tests (e.g., Van Elteren).

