4.7.3 Vital Signs and Anthropometry

Vital signs heart rate (beats/min), and oral temperature (°F), height (cm), weight (kg), body mass index (kg/m²) and anthropometric parameter HAZ will be collected at screening and at month 9.

Observed values at each visit and change from baseline at post-baseline visit will be summarized on the safety population descriptively (n, mean, SD, SE, median, minimum, and maximum) by product group ([Table 14.3.5.1](#)).

All vital signs will be listed ([Listing 16.2.9.1](#)).

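### SAP 3.1 leaves protein off its screening-baseline list, so its default points to a Visit 2 value that is never measured, contrary to SAP 1.2 and protocol 9.3.3 (minor)

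*SAP*

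**What the plan says.** SAP 3.1 has three parts.

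- A list of variables whose screening value is the baseline: height, weight, BMI, HAZ, IDDS and three outputs of the dietary recall. On the recall it reads "carbohydrate, fat and energy from 24 hour dietary recall assessments conducted at screening visit will be considered as baseline".
- A default: "for all other endpoints the baseline value will be the latest pre-dose assessment Visit 2 with a non-missing value".
- A rule for gaps, subject to exceptions stated elsewhere: "if baseline data is missing no derivation will be performed and will be set to missing".

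SAP 1.2 states the dietary objective as "Change from baseline (measured at screening) in energy, protein, carbohydrates and fat consumption, assessed through 24-hour dietary recall survey" and the matching endpoint as "Intake of energy, protein, carbohydrate, and fat from 24-hour dietary recall survey at screening and end of study". Protocol sections 2 and 9.3.3 agree: protein is grouped with the other three nutrients, and the screening value is the covariate.

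SAP 4.4.2 treats the four nutrients alike: "Change from baseline of each assessment will be analysed using the ANCOVA model", with each variable's own baseline as covariate (Table 14.2.12.2).

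For vital signs, SAP 4.7.3 plans that "Observed values at each visit and change from baseline at post-baseline visit will be summarized on the safety population descriptively" (Table 14.3.5.1). Collection is at screening and month 9.

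**The concern.** SAP 3.1 is the section a programmer goes to for the baseline flag. It names three of the four nutrients from the same recall interview and omits the fourth. Protein therefore falls to the default, which points to a visit with no dietary recall. The gap rule then says to derive nothing.

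In the ANCOVA for protein, both the outcome (change from baseline) and the covariate (baseline protein) depend on that value. If SAP 3.1 is followed to the letter, a named secondary variable has no analysable records. If it is not, someone has to override the section that defines baseline, and the SAP does not say so. The trial is open label, so such choices are better settled in writing than in program code.

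**Working it through.** This is a question of definitions. The plan states no figure on this point, so there is none to reproduce. The check compares, for each variable with a planned change from baseline, the baseline visit that SAP 3.1 assigns with the visit before intervention at which the variable is measured. The measurement visits come from the protocol Schedule of Events, the visit lists in SAP 1.1, and SAP 4.7.3.

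| Variable | Baseline visit under SAP 3.1 | Measured before intervention at | Consistent? |
|---|---|---|---|
| Height, weight, BMI, HAZ | Screening (listed) | Screening | Yes |
| IDDS | Screening (listed) | Screening | Yes |
| Energy, carbohydrate, fat | Screening (listed) | Screening | Yes |
| **Protein** | **Visit 2 (default)** | **Screening** | **No** |
| Heart rate, oral temperature | Visit 2 (if the default applies) | Screening | No |
| Lactulose:mannitol, neopterin, salivary IgA | Visit 2 (default) | Visit 2 | Yes |
| Vitamins and trace elements | Visit 2 (default) | Visit 2 | Yes |
| Ferritin, sTfR, CRP, AGP | Visit 2 (default) | Visit 2 | Yes |

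Exactly three variables do not match: protein, heart rate and oral temperature.

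**Protein**

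1. It is not on the SAP 3.1 list, so the default assigns Visit 2.
2. Visit 2 includes no dietary recall, so the assigned baseline is missing for every child.
3. The gap rule then leaves the change value missing. Under SAP 3.1 alone, the number of children with a derivable change in protein is 0.
4. SAP 1.2 and protocol 9.3.3 put the baseline at screening, where it is collected. Under those sections, every child with recalls at screening and end of study has a change value.
5. SAP section 5, which records departures from the protocol analysis, lists no change to the protein baseline. The conflict is therefore undeclared and looks unintended.

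**Heart rate and oral temperature**

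1. Neither is on the list, and neither is measured at Visit 2.
2. The default speaks of endpoints. SAP 1.2 does not list vital signs as endpoints, so it is doubtful that the default covers them.
3. The Table 14.3.5.1 shell has only screening and month 9 rows, fills the change column at month 9, and fills the overall column only at screening. Its programming note restricts the overall column to the baseline visit and names both variables. The shell therefore treats screening as baseline, although no sentence in the SAP text says so.

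**The case against.** The strongest reply is that a SAP is read as a whole. One word is missing from one list, and the endpoint definition in SAP 1.2 supplies it. Protein shares its model and tables with the other three nutrients. An empty protein table would be noticed at once, and the document history shows that the outputs had already been through a dry run. The default sentence is also garbled and could be read as the last non-missing value before dosing, which for protein is the screening value.

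Most of this stands, and it limits the consequence. A reader might infer from SAP 3.1 that change from baseline is lost for every child in protein and in two vital signs. The documents do not support that. The values are collected at both visits, SAP 1.2 and protocol 9.3.3 state the protein baseline, and the vital-signs shell implies one.

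The reply does not remove the contradiction. The generous reading of the default fits poorly. If it meant the last value before dosing, the screening list would be unnecessary, because every variable on it is measured before intervention only at screening. Naming Visit 2 has to do some work, and for protein it gives the wrong visit. That the right answer can be found in another section is a reason to correct the rule.

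**Conclusion.** The point holds as an internal inconsistency of minor severity. As written, SAP 3.1 assigns protein a baseline visit at which it is not measured, in conflict with SAP 1.2 and protocol 9.3.3. It affects one of four nutrients in one secondary objective. Protein change could be derived for no child under SAP 3.1 alone, and nothing is lost if SAP 1.2 governs. For heart rate and oral temperature it is only a consistency point, limited to descriptive safety output.

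The primary analysis is unaffected, because its baseline covariate, IDDS, is on the screening list. No sample size, power or alpha figure changes.

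The conclusion assumes that the Visit 2 default means what it names, and that no dietary recall or vital-sign assessment takes place at Visit 2, as the Schedule of Events and SAP 1.1 both show.

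**What to change.** In SAP 3.1, add protein to the variables whose screening assessment is the baseline, and add heart rate and oral temperature for consistency with Table 14.3.5.1. Reword the default so that the Visit 2 rule applies only to the urine, saliva and blood analytes. This also removes the ambiguous wording about the latest value before dosing.

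With that change, every variable with a planned change from baseline has a baseline at a visit where it is measured. SAP 3.1 then agrees with SAP 1.2, SAP 4.7.3 and protocol 9.3.3. The cost is a sentence or two in the SAP, made before the analysis is run. No model, population or error rate changes, and there is no statistical downside. If the tables are already programmed, confirm that Table 14.2.12.2 takes protein baseline from screening and record that.

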3.2 Subgroups/Stratifications

To control for possible effects of gender, a balanced ratio of boys and girls in the test and the control groups will be targeted. The study will be stratified by gender to recruit a target ratio of 50% girls and 50% boys, with a minimum of 40% of either gender and a maximum of 60% of either gender.

3.3 Centers Pools

This study is conducted in multiple (4) schools, with two schools in each product group.

3.4 Time points and Visit Windows

The time points and visits for this study are defined in the section “Schedule of Events” of the protocol. Any deviation from the study schedule will be reviewed case-by-case basis to determine whether the data should be excluded from the Per Protocol (PP) population. A time window non-compliance listing will be produced for the Blinded Data Review Meeting (BDRM) only.

4 Data Analysis

Data analysis will be performed by Syneos Health. The statistical analysis software used will be SAS Studio version 9.4 or higher.

Prior to database closure a BDRM will be conducted in which various aspects of the trial will be discussed and agreed.

Unless otherwise described below, all listings will be produced for enrolled population.

4.1 Populations for Analysis

Tables described in this section will be produced for enrolled population.

4.1.1 Subject Disposition

Screen failures are defined as participants who consented to participate in the study but were not subsequently enrolled (i.e., excluded basis inclusion/exclusion criteria). A summary of the number of participants screened and the number of screen failures with reasons of their exclusion will be presented ([Table 14.1.1](#)). Percentage of screen failure participants will be based on total number of screened participants. Subject disposition will also be summarized by product group and overall as the number and percentage of participants who completed the study, with the number who discontinue broken down by reason for discontinuation ([Table 14.1.1](#)). The table will also summarize the number and percent of participants assigned to each analysis population (refer to [Section 4.1.3](#)). The percentage will be based on total number of participants enrolled in each product group and overall.

Subject disposition including the participants status (completer, Yes/No), demographic data (age and race), screening date, product groups (including test product and dietary counselling) start date and time, the duration in the study or trial and the specific reason for discontinuation, will be listed for enrolled population ([Listing 16.2.1.1](#)) by product group.

Duration in the study or trial will be calculated using the formula below –

$(\text{Date of completion/withdrawal minus date of baseline visit})+1$

Subject disposition information for non-enrolled participants will include subject number, demographic information (age and race), screening date, reason for screen failure and details if any regarding the reason for screen failure ([Listing 16.2.1.2](#)).

4.1.2 Protocol Deviations

Protocol deviations will be tracked by the study team throughout the conduct of the study. Data will be reviewed prior to un-blinding and closure of the database to ensure all important deviations are captured and categorized. Participants with major protocol deviations (defined below) will be excluded from the PP population.

Major deviations of the protocol procedures identified as liable to influence the efficacy outcomes of the study may include, but will not be necessarily limited to the following:

- Violation of inclusion or exclusion criteria
- Significant non-compliance with assigned treatment
- Use of prohibited treatment or medication before or during the study
- Any other reason identified which may affect the efficacy assessments

The number and percentage of participants with any major protocol deviations will be presented by product group and overall (Table 14.1.2) and listed (Listing 16.2.2.1). Any minor protocol deviations will be listed similarly (Listing 16.2.2.2).

4.1.3 Analysis Populations

Six analysis populations are defined.

| Population | Definition / Criteria | Analyses Evaluated |
|--------------------------|---|---|
| All Screened Subjects | 
 All participants who enter the study and sign the informed consent form. This population includes screen failures as well. | 
 Disposition, AE listing |
| Enrolled Population | 
 All participants who attended baseline visit will be considered in enrolled population. | 
 Protocol deviations, AE, efficacy, demographic characteristic, disposition and medical history listings |
| Safety | 
 Comprise of all participants who received at least one dose of study product (i.e. either only dietary counselling or both supplement and dietary counselling) during the study. This population will be based on the product to which the participant was planned to receive. | 
 Safety |
| Intent-To-Treat (ITT) | 
 All participants in the safety population with any post-treatment assessment (SPWR is considered as post-treatment assessment) will be included in Intent-to-treat (ITT) population. This population will be based on the product to which the participant was planned to receive. | 
 Efficacy |
| Modified Intent-To-Treat | 
 All participants in the ITT population who have completed entire study of 9 months | 
 Primary, Secondary |

| Population | Definition / Criteria | Analyses Evaluated |
|--------------|--|--|
| (mITT) | 
(i.e., attended up to end study visit) will be included in modified intent-to-treat (mITT) population.
 
 This population will be based on the product to which the participant was planned to receive. | Exploratory Efficacy |
| Per-Protocol | 
 Participants who have all post-treatment assessment and do not have any major protocol deviations that would affect efficacy assessments. Participants with major protocol deviations will be excluded. Depending on the nature of the major protocol deviation and impact on the efficacy variable (s), subjects will be either completely excluded from PP population or only partially excluded from the PP analyses. This will be determined on a case-by-case basis. | 
 Efficacy |

The primary population for assessment of efficacy will be the mITT Population. A PP analysis will be performed on the primary variable if more than 5 % of the subjects in the mITT Population are excluded from the PP Population.

Participants excluded from any of the analysis populations will be listed ([Listing 16.2.3.1](#)), with the reason for exclusion.

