As this study is using cluster randomisation, and design effect (DE) needs to be considered for sample size calculations. Scientific literature suggests, DE due to cluster sampling strategy can be assumed to be 1.5 [Rosner, B, 1986]. Same has been assumed in one study, which used three-stage systematic cluster sampling [Dandona R *et al*, 2008].

Using the following formula from Hemming *et al*, 2011:

$$N^* = N \times DE$$

Where N*=Number of participants required for cluster randomised trial

 GlaxoSmithKline	Document Name	Clinical Study Protocol 204477		
	Type	Version	Document Identifier	Effective Date
	eldo_clinical_doc	5.0; Most-Recent; Effective; CURRENT	090032d580daa95e	10-Oct-2017 06:16:49
	Reason For Issue	Auto Issue		

N = Number of participants required for individual randomisation

DE = Design Effect

And assuming DE to be 1.5, the number of evaluable participants completing the study required would be 323 per arm (Total=646).

To allow for 30% drop-out rate, a total of 924 participants will be randomised.

Approximately 1300 participants will be screened to randomise approximately 924 participants in order to obtain 646 participants completing the study.

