9.2. General Considerations

9.2.1. Definition of Analysis Populations

All participants who receive the study product will be considered evaluable for the safety population.

All participants in the safety population with any post-treatment assessment will be included in Intent-to-treat (ITT) population. ITT population will be the primary population for efficacy analysis.

Per protocol (PP) population will consist of participants who have all post-treatment assessments and do not have any protocol violations that would affect efficacy assessments. PP analyses will be performed only if there is more than 5% difference between number of study participants in ITT and PP population. A final decision on whether a PP analysis will be performed will be made prior to study un-blinding.

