9.2.3. Criteria for Assessing Efficacy

The study will be deemed to be successful if a statistically significant decrease is demonstrated in number of ill days during nine (9) months of intervention in the test product group compared to the control product of the study.

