9.3.2. Primary Analyses

The primary efficacy variable of the study is the number of ill days. The number of ill days is defined as number of days a subject is ill because of GI and/or respiratory illnesses as diagnosed by study physician, as per the criteria defined in Section 6.11.1 and 6.11.2, over the intervention period.

For this variable, primary analysis will be performed on participants in ITT population who have completed the entire study for 9 months.

The null hypothesis of interest is:

H₀: There is no difference in the number of ill days.

The alternative hypothesis of interest is:

H₁: There is a difference in the number of ill days.

The number of ill days will be summarised in terms of number (N), mean, standard deviation, minimum, and maximum for both the treatment groups.

The number of ill days will be analysed using the analysis of variance (ANOVA). The ANOVA will have treatment, cluster (school), and gender as fixed effects.

Adjusted means, 95% confidence intervals, within treatment p-values for each treatment group, treatment group difference, 95% confidence interval of the difference and the between-treatment p-values based on the statistical model described above will also be presented.

All statistical tests of hypotheses will be two-sided and will employ a level of significance of $\alpha = 0.05$.

The simulated data used for the sample size calculations were based upon the assumption of a Poisson distribution per study treatment. However, on observation of these simulated data, it was considered that these Poisson distributions were not heavily skewed and, as a result, normal distributions may be assumed. Consequently, a normality assumption has been adopted for both the generation of sample size and the intended approach to the statistical analysis. However, the assumptions of normality and homogeneity of variance will be investigated and violation of these assumptions may be overcome using suitable transformation (for example, log or square root). If transformed data is also non-normal, then alternative analyses relevant to Poisson distributed data will be investigated (further details will be

 GlaxoSmithKline	Document Name	Clinical Study Protocol 204477		
	Type	Version	Document Identifier	Effective Date
	eldo_clinical_doc	5.0; Most-Recent; Effective; CURRENT	090032d580daa95e	10-Oct-2017 06:16:49
	Reason For Issue	Auto Issue		

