9.3.3. Secondary Analyses

Following secondary efficacy variables will be analysed for both completers (those who completed entire 9 months of study) and ITT population.

The secondary efficacy variables are:

- Frequency of GI and respiratory illnesses defined as total number of illness episodes of GI and/or respiratory illnesses, divided by duration of intervention, where each episode is defined as each incidence of illness followed by at least 3 symptom free days (Section 6.11.2).

The same model outlined above for primary outcome variable will be used for this secondary outcome.

- Severity of GI and respiratory illnesses (Mild, moderate, or severe intensity as captured in DF) (See Section 6.11.2 for details on capturing severity of illness).

This will be captured by study physician as per severity grading outlined in Appendix 5. Frequencies of intensity (Mild, moderate, or severe) by treatment groups will be compared using chi-square test (if frequencies are greater than 5%). If frequencies are $\leq 5\%$ in any treatment groups, then these will be compared using Fisher's exact test between treatment groups.

- School absenteeism due to GI and respiratory illnesses as identified from DF.

The same model outlined above for primary outcome variable will be used for this secondary outcome.

- Change from baseline (measured at screening visit) in BMI.

This will be analysed using an analysis of covariance (ANCOVA) model. The model will include the fixed factors for treatment, cluster (school) and gender; baseline BMI assessment recorded at screening visit as covariate.

- Change from baseline in gut integrity/health as measured by Lactulose:Mannitol test and Urinary Neopterin test defined in Section 6.9.1.1 respectively.

 GlaxoSmithKline	Document Name	Clinical Study Protocol 204477		
	Type	Version	Document Identifier	Effective Date
	eldo_clinical_doc	5.0; Most-Recent; Effective; CURRENT	090032d580daa95e	10-Oct-2017 06:16:49
	Reason For Issue	Auto Issue		

These will be analysed using an ANCOVA model. The model will include the fixed factors for treatment, cluster (school) and gender; baseline gut integrity/health assessment at baseline as covariate.

- Change from baseline in salivary IgA as defined in Section 6.9.1.2.

This will be analysed using an ANCOVA model. The model will include the fixed factors for treatment, cluster (school), and gender; baseline salivary IgA assessment at baseline as covariate.

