4.8 Analysis of Other Variables

Not applicable.

5 Changes to the Protocol Defined Statistical Analysis Plan

Any changes from the originally planned statistical analysis specified in the protocol (Dated: 10 October 2017) are outlined in Table 1.

Table 1 Changes to Protocol Defined Analysis Plan

| Protocol | Reporting & Analysis Plan |
|----------|---------------------------|
|----------|---------------------------|

| Statistical Analysis section | Statistical Analysis Plan | Rationale for Changes |
|---|--|---|
| 
 4.1.3 | 
 Enrolled population defined Modified ITT population defined | 
 Since this study uses cluster randomization and not individual participant's randomized so randomized population cannot be defined. Instead enrolled population defined. To allow the exclusion of some enrolled participants in a justified way (such as participant who were deemed ineligible after enrolment or certain participants who never started treatment). |
| 
 4.4.1 and 4.4.2 | 
 Primary, secondary and exploratory analysis will be done on mITT population. | 
 Primary analysis should be done on participants those who are presented entire study duration. Secondary and exploratory outcome data (particularly those involving analysis on human biological samples), are available only after End of study visit (visit 10). ANOVA model for analysis of ferritin, serum-transferrin receptor (sTfR), is modified. |
| 
 9.2.1 | 
 PP analysis will be performed in case there is a 5% difference observed between number of subjects in mITT (instead of ITT) and PP. | 
 This change has been incorporated since mITT is primary population of analysis |

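### The primary test uses nine-month completers only although protocol 9.2.1 names ITT; dropouts' nine-month data enter only a supportive MMRM that assumes missing at random, and nothing tests that assumption

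*SAP*

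**What the plan says.** The protocol gives two answers. Section 9.2.1 states: "ITT population will be the primary population for efficacy analysis". Section 9.3.2 then says of the primary variable: "primary analysis will be performed on participants in ITT population who have completed the entire study for 9 months". SAP 4.1.3 labels that completer set mITT ("All participants in the ITT population who have completed entire study of 9 months") and settles the matter in its favour: "The primary population for assessment of efficacy will be the mITT Population". SAP 4.4.1.2 runs the primary model on it. The success rule in protocol 9.2.3 rests on this one test: "The study will be deemed to be successful if a statistically significant decrease is demonstrated in number of ill days".

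SAP Section 5, Table 1 declares the change and gives this reason: "Primary analysis should be done on participants those who are presented entire study duration". It adds that secondary and exploratory outcome data, biological samples in particular, exist only after Visit 10. It also says mITT allows exclusion of children found ineligible after enrolment or never treated.

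For secondary variables protocol 9.3.3 says: "Following secondary efficacy variables will be analysed for both completers (those who completed entire 9 months of study) and ITT population". SAP 4.4.2 keeps mITT only.

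Dropouts are not ignored altogether. SAP 4.1.1 tabulates disposition by group, and SAP 4.2 gives baseline tables for both ITT and mITT. SAP 4.4.1.3 plans an MMRM of ill days on ITT as a sensitivity analysis. SAP 4.6 analyses ill days over 3 and 6 months in ITT children who reached those points. Protocol 9.2.5 and SAP 4.4.3 rule out imputation.

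**The concern.** Completion is a post-allocation event. The trial is open label, and only the test arm takes a product twice daily for nine months, so the reasons for leaving could differ between arms. Comparing completers with completers then compares two selected groups.

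The data needed to limit this already exist. Ill days come from weekly physician reviews with start and end dates (protocol 6.11.3, 6.12 and the Diagnosis Form in Appendix 5). A child who leaves in month 6 has about six months of usable illness history, and the primary test discards it.

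The SAP's reasons do not support that. Children who never started treatment are already outside Safety, and therefore outside ITT. Dependence on Visit 10 fits blood, urine and saliva measures. It does not fit frequency, which SAP 4.4.2 already divides by each child's own follow-up, or absenteeism, which is recorded weekly.

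The target difference is small (0.7 day), so a moderate imbalance among dropouts would be a large share of it.

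**Working it through.** **Inputs.** From protocol 9.1 and SAP 1.4: control mean 7.0 (SD 2.65), test mean 6.3 (SD 2.51), two-sided 5%, 80% power, design effect 1.5, 30% dropout. The plan states: "To allow for 30% drop-out rate, a total of 924 participants will be randomised".

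**The plan's own figures reproduce.**
- Pooled SD = √((2.65² + 2.51²)/2) = 2.581. The exact t calculation for a difference of 0.7 gives 215 per arm (power 80.1%).
- 215 × 1.5 = 322.5, rounded up to 323 per arm, 646 in total.
- 323/0.70 = 461.4, rounded up to 462 per arm, 924 in total.

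**Data left out of the primary test.** 924 − 646 = 278 children (30.1%), or 139 per arm. This is a planning figure and an upper bound on ITT children omitted: a child who leaves before any weekly review has no post-treatment assessment and is not in ITT either. If the 278 are followed for a fraction f of nine months (an assumption), unused child-months are 278 × 9 × f, set against 646 × 9 = 5,814 from completers:

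| f | Unused child-months | Share of recorded follow-up |
|---|---|---|
| 1/3 | 834 | 12.5% |
| 1/2 | 1,251 | 17.7% |
| 2/3 | 1,668 | 22.3% |

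**Bias of the completer comparison.** In one arm let d be the dropout fraction, C the completers' mean, and g the dropouts' minus completers' mean ill days over nine months. The whole-arm mean is (1 − d)C + d(C + g) = C + dg, so the completer mean is off by −dg. For test minus control the bias is −(dT·gT − dC·gC); a negative value favours test. The documents give no between-arm values, so all of these are assumptions:
- 30% dropout in both arms, gT = gC: 0.
- 30% in both arms, gT − gC = +1 day: −0.30 day (0.30/0.70 = 43% of target).
- 30% in both arms, gT − gC = −1 day: +0.30 day.
- Common g = 1 day, dropout 35% test and 25% control: −0.10 day.
- Common g = 1 day, dropout 40% test and 20% control: −0.20 day.

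**What would tip the result.** Suppose dropout is equal by arm (139/462 = 0.301), completers show −0.7, and the planned SDs and design effect hold. Let D be the test-minus-control difference among dropouts. The whole-population difference is 0.699 × (−0.7) + 0.301 × D, with SE = 2.581 × √(2/(462/1.5)) = 0.208.
- D = 0 gives −0.49 (z = −2.35).
- Significance is lost when D exceeds (0.489 − 1.96 × 0.208)/0.301 ≈ +0.27 day. As D = −0.7 + (gT − gC), that is gT − gC of about 0.97 day.
- The difference reaches zero at D ≈ +1.63 days.

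**What a person-time rate would recover.** With a constant illness rate and 30% dropout in each arm, a pooled rate per nine months leaves a residual error, per 1-day difference in g, of 0.3 − 0.3f/(0.7 + 0.3f). This is 0.175, 0.124 and 0.078 day for f = 1/3, 1/2 and 2/3, against 0.30 for completers only. The error is reduced, not removed. An overdispersed model weights children differently, so its residual will not match these figures exactly.

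**Shorter-window analyses.** If dropout is uniform over time, 278 × 3/9 ≈ 93 children have left by month 3 and 278 × 6/9 ≈ 185 by month 6. The 3- and 6-month analyses therefore also condition on staying, and they do not address the nine-month total.

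**The case against.** The case for the plan has substance. Section 9.3.2 is the rule specific to this variable and 9.2.1 the general one; the SAP chooses openly between them and declares the choice. The sample size counts children who complete, so a completer analysis matches the design. A nine-month total is also simple to interpret and, unlike a rate, needs no assumption that illness is stable over follow-up. All of that stands as a defence against a charge of concealment. It does not reconcile the two protocol sentences or make completers free of selection.

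Three stronger readings are tempting and are not supported.
- *A reader might infer that no analysis examines dropouts.* SAP 4.4.1.3 plans an ITT MMRM expressly as a sensitivity analysis, with its own Month 9 table, and SAP 4.6 adds the 3- and 6-month ITT analyses. The gap is narrower: nothing departs from missing at random.
- *A reader might infer that the MMRM's Month 9 contrast concerns only the last three months*, and so targets 0.70/3 = 0.23 day. The title of Table 14.2.2.1 and SAP 4.6 point to Months 3, 6 and 9 with counts over the whole period. What is missing is an explicit statement and a rule for part-observed intervals.
- *A reader might infer that the result will be biased towards the product.* The direction is open, and the 0.30-day figure needs an assumed 1-day differential, which exceeds the target effect itself.

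Replacing the primary model outright is also debatable. A random-effect count model on four schools is not obviously more robust, and if illness rates vary over the nine months while dropout timing differs by arm, a rate adds a bias that the completer total does not have.

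**Conclusion.** The concern holds in a limited form. The textual points are certain: protocol 9.2.1 conflicts with 9.3.2 and SAP 4.1.3, the success test uses completers only, and SAP 4.4.2 drops planned ITT secondary analyses for a reason that does not fit frequency or absenteeism. The primary test omits the recorded ill days of up to about 278 of 924 children, if dropout is as planned.

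The size of any bias cannot be known from the documents. It is zero when dropout and dropouts' relative illness burden match across arms. The 0.30-day shift and the +0.27-day tipping value show sensitivity under stated assumptions and do not predict the outcome. What the plan lacks is a way to show readers, once data are in, how far the conclusion depends on children who left. This should be fixed before analysis.

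**What to change.** 1. Reconcile protocol 9.2.1 with 9.3.2 and SAP 4.1.3, so that one primary population is named throughout.
2. Prespecify an ITT analysis, by allocated school, of ill days per time at risk. Use an overdispersed count model with the log of days from first dietary counselling session to last weekly review as offset (the same start in both arms), school handled as in SAP Amendment 1, plus gender and baseline IDDS. Report it per nine months beside the completer total: at least as the main sensitivity analysis, and as primary if 9.2.1 is to stand.
3. Restore the ITT analyses of frequency and absenteeism from protocol 9.3.3, with absenteeism per time at risk.
4. Add one tipping-point analysis that varies dropouts' unobserved ill days separately by arm.
5. In SAP 4.4.1.3, state the MMRM visits, whether counts are cumulative, and how a part-observed interval is counted.

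**Cost.** SAP text, a protocol clarification and some programming; no new data. Illness dates are on the Diagnosis Form and the SAP already derives follow-up time. SAP 4.4.1.2 names Poisson regression in Proc Genmod, but a random school effect needs a different procedure.

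**Limits.** The rate assumes stable illness over follow-up. It reduces selection without removing it: ITT itself requires a post-treatment assessment, and children are screened after schools are allocated. The small number of schools is a separate matter that this does not address.
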